5.1 INCLUSION CRITERIA

Participants are eligible to be included in the study only if all of the following criteria apply:

Age

I 01. 18 to 70 years of age inclusive with the diagnosis of asthma based on Global Strategy for Asthma Management and Prevention (GINA) 2019 ([1](#)) at the time of signing the informed consent.

Type of participant and disease characteristics

I 02. History of ≥ 1 exacerbation(s) in the previous year before V1.

Exacerbation is defined as deterioration of asthma that results in emergency treatment, hospitalization due to asthma, or treatment with systemic steroids.

I 03. Uncontrolled moderate-to-severe asthma (ACQ-5 ≥ 1.5) at V1 and V2, prior to randomization.

I 04. Pre-bronchodilator FEV₁ $\leq 80\%$ of predicted normal at V1 and V2, prior to randomization.

I 05. Exhibit bronchodilator reversibility ($\geq 12\%$ and 200 mL improvement in FEV₁ post SABA administration) during screening, prior to randomization.

I 06. Blood eosinophil ≥ 300 cells / μ L and FeNO ≥ 25 ppb during screening and prior to randomization.

NOTES:

- Historical values of blood eosinophil count meeting the eligibility criterion measured within 6 months prior to SV1 in the absence of OCS treatment are allowed.
- FeNO value to be checked for eligibility at V2 as well.

I 07. Existing treatment with medium to high dose ICS in combination with a second controller (eg, LABA, LTRA) \pm a third controller. The dose regimen should be stable ≥ 1 month prior V1 and during screening.

I 08. Willing and able to comply with all clinic visits and study related procedures.

Weight

Not applicable.

Sex

I 09. Male and Female

Contraceptive used by men or women should be consistent with local regulations regarding the methods of contraception for those participating in clinical studies.

Female participants of childbearing potential are eligible to participate if they agree to use a highly effective method of contraception consistently and correctly during the intervention period and up to 12 weeks after last dose of study intervention or until the participants switch to commercialized dupilumab (or other biologic products), whatever comes first, as described in [Section 10.4](#) (Appendix 4).

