A high mucus score (plugs in ≥ 4 segments) occurred in 67% of subjects with asthma with FEV₁ of less than 60% of predicted volume, 19% with FEV₁ of 60% to 80%, and 6% with FEV₁ greater than 80% ($P < 0.001$). N=146, among those 96 were severe asthma participants (65%) (39).

Functional Respiratory Imaging can accurately assess the regional airway closures induced by mucus plugs and the re-opening of airways due to intrapulmonary percussive ventilation in COPD participants (40).

Airway wall thickness

Asthmatics have increased airway wall volumes due to inflammation compared to healthy individuals.

The airway wall volume/airway lumen ratio parameter can be derived from the FRI parameters airway wall volume and airway volume. Airway wall thickness can be derived from this as well (and can be shown in discreet locations).

After a treatment with ICS in asthma an increase in airway lumen volume (iVaw) and a reduction in airway wall volume (iVaww) can be observed. The effect size of iVaw is larger than effect size iVaww due to the better resolution of iVaw in HRCT. Similar findings were observed by Haldar et al when studying Mepolizumab (41).

Lobar volumes

By identifying and grouping the voxels that represent the air in the lungs, the lung volume (L) can be determined from the scans at both FRC and TLC. During segmentation, identifying the fissure planes on the CT images and using these surfaces as cutting objects can separate lung lobes. Therefore, not only the total lung volume is determined, but also the volume of each lobe individually, which allows to pick up substantial regional physiological changes of the airways and the lobe volumes.

The HRCT scans assessment will be performed by central reading. Further details on the procedure will be provided in a separate instructions manual. The wash out period of asthma controllers and rescue medication before HRCT scan is detailed in the [Table 4 \(Section 8.1\)](#).

If HRCT scan cannot be performed at D1 due to logistic reasons, it can be scheduled the next day. In this particular situation the investigator should ensure that the IMP loading dose is administered after the HRCT scan, at D1+1 day.

At visits, the HRCT scan can be done before spirometry or before post-BD FEV1 or after spirometry (in the latter case the wash-out period of SABA should be ensured), as per Investigator's decision.

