Primary objective: To assess the effect of dupilumab on lung inflammation and related changes in airway volumes detectable by functional respiratory imaging.					
Primary endpoints	Proportion of participants achieving FeNO <25 ppb at Week 24	ITT	
 Discontinuation of study intervention due to Covid-19 pandemic^a (IcEv1), off-study intervention data will be set as missing (hypothetical strategy). Discontinuation of study intervention not due to Covid-19 pandemic (IcEv2), all data collected following schedule after the study intervention discontinuation will be used in the analysis (treatment policy strategy). 		
Achievement of FeNO <25 ppb at Week 24 will be analyzed using a Cochran-Mantel-Haenszel (CMH) test adjusted by stratification factors (region and ICS dose level). Corresponding odds ratios and 95% CI with p-value will be reported.
 
Missing data at Week 24 will be considered as non-responders.

Secondary objective: To evaluate the effect of dupilumab at Week 24 on bronchodynamics, hyperinflation, airway resistance, airway wall volume, ventilation defects and mucus plugging derived from high-resolution computed tomography (HRCT) scans, patient-reported outcomes, FeNO and spirometry.					
Percent change from baseline to Week 24 in untrimmed distal specific airway volume ([s]iVaw) at total lung capacity (TLC)	ITT	
 Discontinuation of study intervention due to Covid-19 pandemic^a (IcEv1), off-study intervention data will be set as missing (hypothetical strategy). Discontinuation of study intervention not due to Covid-19 pandemic (IcEv2), all data collected following schedule after the study intervention discontinuation will be used in the analysis (treatment policy strategy). 		
A mixed effect model for repeated measures (MMRM) under the missing at random (MAR) framework will be used. The MMRM will use percent change from baseline in untrimmed distal [s]iVaw at TLC up to Week 24 as the response variable, and will include study intervention, baseline value, region, ICS dose level, visits, study intervention by visit interaction, and baseline by visit interaction terms all as fixed effects.
 
Region, ICS, study intervention and visits will be considered as categorical parameters. No explicit imputation will be done for missing data. Baseline values corresponding to the outcome variables should be used.
	

Endpoint Category (estimand)	Estimands			

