8. EFFICACY ANALYSIS

Efficacy analyses will be performed on the ITT analysis set.

Participants will be analyzed for efficacy according to the study intervention group to which they are allocated by the IRT according to the randomization schedule at the randomization visit (as randomized), irrespective of the study intervention actually received.

For all efficacy analyses, time window will be used to assign the visit (see [Section 15.5](#)).

For the analysis of primary objective in the study intervention period,

- The null statistical hypothesis tested is that 1) the proportion of participants achieving response of FeNO <25 ppb at Week 24 is the same between dupilumab and placebo group; 2) the percentage change from baseline in untrimmed distal [s]iVaw is the same between dupilumab and placebo group.
- The alternative statistical hypothesis tested is that 1) the proportion of participants achieving response of FeNO <25 ppb at Week 24 is different between dupilumab and placebo group; 2) the percentage change from baseline in untrimmed distal [s]iVaw is different between dupilumab and placebo group.

In order to preserve the type I error at 0.05 level for the two primary endpoints, a hierarchical testing procedure will be adopted. The tests will be performed in this order:

1. Proportion of participants achieving response of FeNO <25 ppb at Week 24
2. Percentage change from baseline to Week 24 in untrimmed distal [s]iVaw at TLC

All efficacy measurements collected during the study will be considered for analyses, including those obtained after IMP discontinuation, except if study intervention discontinuation was due to the COVID-19 pandemic. Refer to [Table 2-2](#) for more details.

For efficacy endpoints where a change from baseline or percent change from baseline is assessed, only the participants with a baseline and at least one post-baseline value available will be included in the analysis model (number of participants included in the analysis model reported in the table). All available results will be included in the descriptive statistics.

Line plots for change and percent change from baseline will be presented by study intervention group, displaying the LS mean and SE at each visit. These plots will be provided for the primary and all secondary continuous endpoints.

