Note: baseline value corresponds to the baseline value of the variable being analyzed. In case of variables in the percentage scale, this will be the baseline value on the raw scale.

Data may be logarithmically transformed prior to analysis if extreme skewness was observed based on blinded data review.

If the MMRM model under unstructured correlation matrix fails to achieve convergence due to complexity of model specification, different covariance structures will be used according to the following order till convergence is achieved:

1. Heterogeneous Toeplitz (TOEPH)
2. Homogeneous Toeplitz (TOEP)
3. First-Order Autoregressive [AR(1)]
4. Compound Symmetry (CS)

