8.2.3. Functional Respiratory Imaging (FRI)

FRI secondary endpoints (see [Section 15.10](#)) will be summarized in terms of actual value and change from baseline or percent change from baseline to each post-baseline visit (Week 4 and Week 24).

In addition, at each post-baseline visit, the change from baseline or percent change from baseline will be modelled using the same MMRM model as the one used for the primary end point relating to untrimmed distal [s]iVaw at TLC. Baseline value will be the one of the variable being analyzed and, in case of variables in the percentage scale, it will be the baseline value on the raw scale. LS mean of each study intervention group, LS mean difference between the dupilumab and placebo groups, and the corresponding SEs and 95% CIs will be provided at all scheduled visits. The p-value corresponding to the LS mean difference will be provided at Week 24 only.

The same strategy as for MMRM model for primary endpoint untrimmed distal [s]iVaw will be used for the selection of the covariance structure if MMRM under unstructured correlation matrix fails to achieve convergence.

FRI secondary endpoints are the following:

- Untrimmed distal [s]iVaw at FRC (percentage change from baseline)
- Trimmed distal [s]iRaw at TLC (percentage change from baseline)
- Trimmed distal [s]iRaw at FRC (percentage change from baseline)
- Global lung iVlobes at TLC (percentage change from baseline)
- iV/Q at TLC (change from baseline) for lower and upper lung
- HRCT based IAD (change from baseline) for lower and upper lung
- Global lung UCSF mucus scoring (change from baseline)

* Data may be logarithmically transformed prior to analysis if extreme skewness was observed based on blinded data review.

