8.2.5. Multiplicity issues

The overall type-I error rate will be controlled at the two-sided 0.05 level using a hierarchical testing procedure. The primary endpoints will be tested sequentially in the order described in [Section 8](#). The secondary endpoints will be tested following the hierarchical testing procedure with a pre-specified order, that is, inferential conclusions about successive secondary endpoints require statistical significance at 0.05 significance level of the previous one.

The following secondary endpoints will be included in the multiplicity adjustment scheme and tested in the following order:

- Change from baseline to Week 24 in global lung UCSF Mucus Scoring
- Percent change from baseline to week 24 in trimmed distal [s]iRaw at TLC

Each endpoint will be tested at 0.05 (two-sided) level of significance. If at any step the null statistical hypothesis of no study intervention difference is not rejected, the endpoints listed after that step will be reported at nominal level, otherwise will be technically eligible for being declared significant.

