As the visible area on the scanner can vary from one visit to another, the results can be trimmed (use only generations of airways that are visible in all the scans for each segment) in order to keep only the area common to the different visits, or untrimmed (use all the generations visible at the particular study visit scan for each segment). Trimmed and untrimmed data will be available.

Specific Airway Volume ([s]iVaw):

(s)iVaw is the change of volume of the airways (in mL), taking into account the lung volume changes (in L) as well. It corresponds to the ratio between the airway volume (iVaw) and the lobar volume.

Specific Airway Resistance ([s]iRaw):

(s)iRaw is defined as the pressure drop over the flow rate of the fluid. The unit is [kPa/(L/s)] or [kPa*s/L].

Mucus score:

University of California, San Francisco (UCSF researchers (John Fahy's research group) have developed a new method to measure the burden of intraluminal mucus using Multi-detector Computed Tomography (MDCT) by quantifying the number of bronchopulmonary segments that are completely occluded with mucus.

Airway wall volume:

Asthmatics have increased airway wall volumes due to inflammation compared to healthy individuals. The airway wall volume/airway lumen ratio parameter can be derived from the FRI parameters airway wall volume and airway volume. Airway wall thickness can be derived from this as well (and can be shown in discrete locations).

Lobar volumes:

By identifying and grouping the voxels that represent the air in the lungs, the lung volume (L) can be determined from the scans at both FRC and TLC. During segmentation, identifying the fissure planes on the CT images and using these surfaces as cutting objects can separate lung lobes. Therefore, not only the total lung volume is determined, but also the volume of each lobe individually, which allows to pick up substantial regional physiological changes of the airways and the lobe volumes.

Airway dilation:

Airway dilation is defined as the difference between the trimmed airway volume at week 24 and the trimmed airway volume at baseline.

Airway recruitment:

Airway recruitment is defined as the difference between the untrimmed airway volume at week 24 and the untrimmed airway volume at baseline and the airway dilation.

Pi10:

Pi10 represents the average airway wall thickness normalized to a ‘theoretical’ airway lumen of 10-mm inner perimeter. This endpoint is calculated from a segmental level (distal airway zone).

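### Does the loosely worded log-transform option in SAP 8.1.1 and 8.2.3 undermine the gated tests, above all the mucus score, which can be 0?

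*SAP*

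**What the plan says.** The sentence "Data may be logarithmically transformed prior to analysis if extreme skewness was observed based on blinded data review" closes the description of the [s]iVaw model in SAP 8.1.1. It returns in SAP 8.2.2 for FeNO change, in SAP 8.2.3 as a note opened by an asterisk below the list of imaging secondaries, and in protocol 9.4.1 without restriction to any endpoint. It is absent from SAP 8.2.1 (FEV1) and 8.2.4 (ACQ-7).

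In the text available for this review no endpoint in the 8.2.3 list carries the asterisk. The mark may have been lost when the PDF was read.

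The first secondary in the testing order of SAP 8.2.5 is "Change from baseline to Week 24 in global lung UCSF Mucus Scoring"; trimmed distal [s]iRaw at TLC follows it. SAP 15.10 describes the mucus score as "quantifying the number of bronchopulmonary segments that are completely occluded with mucus", and SAP 8.1.4 bands it 0-3.5 and 4-20.

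The default analysis of each continuous gated test is fully written: an MMRM on percent change for [s]iVaw and [s]iRaw, and on change for the mucus score, with covariates and covariance structure named.

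**The concern.** The trigger is a phrase rather than a rule. The SAP does not say which skewness statistic is used, how large it must be, or whether the measured value, the change or the percent change is logged.

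For the mucus score the option cannot be carried out literally once anyone scores 0, so an offset would have to be chosen. That test gates [s]iRaw.

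If [s]iVaw were logged, other parts of the SAP would no longer match the analysis. Table 2-2 states that "The MMRM will use percent change from baseline in untrimmed distal [s]iVaw at TLC up to Week 24 as the response variable", and the null hypothesis in section 8 is that "the percentage change from baseline in untrimmed distal [s]iVaw is the same between dupilumab and placebo group". The ANCOVA in 8.1.5 is also written for percent change.

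Skewed mucus scores are plausible. Protocol 8.1 reports that a score of 4 or more "occurred in 67% of subjects with asthma" whose FEV1 was below 60% predicted, and in 19% of those at 60-80%. Entry requires FEV1 at or below 80% "of predicted normal at V1 and V2, prior to randomization". At stake would be an endpoint scale, and hence power, left open at a confirmatory test.

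**Working it through.** **1. Tests affected.** The hierarchy has four tests. FeNO response is binary, so a log does not apply. [s]iVaw at TLC, the mucus score and [s]iRaw at TLC remain: at most 3 of 4. Whether the mucus score is really among them depends on the asterisk. SAP 8.2.1 to 8.2.4 assign the option section by section, and protocol 9.4 describes itself as a summary.

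**2. [s]iVaw and [s]iRaw.** The plan's figure is about 64% power with 87 evaluable participants (58 and 29). The assumed difference and SD are blacked out, so it cannot be reproduced forward. Solving the noncentral t backwards, with noncentrality d/√(1/58 + 1/29), gives d ≈ 0.533 SD. If percent change is normal, the share at or below zero is Φ(0) = 50% on placebo (mean 0 assumed) and Φ(-0.533) ≈ 30% on dupilumab. Percent change itself therefore cannot be what is logged. The measured values can be: SAP 15.10 defines [s]iVaw as airway volume over lobar volume, and resistance is likewise positive. ln(visit/baseline) = ln(1 + percent change/100) always exists and is the ordinary reading of logging the data.

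**3. Mucus score.** ln(0) does not exist, and change is zero or negative for anyone stable or improved, so a log needs ln(score + c). On the protocol's figures, 100 - 67 = 33% to 100 - 19 = 81% would score below 4. Below 4 is not 0, however, and a skewed baseline score does not establish a skewed change, which is the default response. The documents give no share of zeros.

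**4. Type I error, mucus score.** Simulated ANCOVA, 58:29, two-sided 0.05, no effect:
- Beta-binomial scores fitted to the 67%/19% figures: 4.3-5.3% untransformed, 4.4-5.4% for ln(score + 1).
- Gamma-Poisson scores: 4.3-5.4% for each of untransformed and offsets 0.01, 0.5 and 1. The four verdicts disagreed in about 9% of runs, which matters only if the choice follows the p-value. Blinded review excludes that.

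**5. Power, mucus score.** Distributions are assumed, and the untransformed model is set near 64% (borrowed from [s]iVaw, since none is stated for this endpoint). Results with half of participants below 60% FEV1:

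| Clearing pattern | Untransformed | ln(score + 0.5) | ln(score + 1) | ln(score + 1) minus untransformed |
|---|---|---|---|---|
| Uniform by segment | 63.5% | 34.7% | 42.2% | -21.3 |
| Variable by person | 64.5% | 49.3% | 55.3% | -9.2 |
| Half of dupilumab arm responds | 63.2% | 49.6% | 56.7% | -6.5 |
| Multiplicative person noise | 63.9% | 51.4% | 56.3% | -7.6 |
| Complete clearing in 31% of dupilumab arm | 62.1% | 85.7% | 83.9% | +21.8 |

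Over all 18 combinations of pattern and severity mix, ln(score + 1) minus untransformed runs from -29 to +22 points, and ln(score + 0.5) from -35 to +24. Untransformed and ln(score + 1) verdicts differ in 18-31% of trials. That range supposes the option is always invoked and the test always reached. In the same simulations pooled |skewness| exceeds 1 in 5-100% of trials and 2 in 0-98%. The test is formally reached only after both primaries succeed, the second at about 64% on the planning assumptions.

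**6. Power, [s]iVaw.** Log minus raw, assumed log correlation 0.7:
- Clean log-normal: SD 0.25, 67.2 - 64.4 = +2.8; SD 0.35, 70.3 - 65.0 = +5.3.
- 5% of Week 24 values halved (SD 0.15): 54.4 - 63.6 = -9.2.
- Log SD 30% larger on dupilumab (SD 0.35): 54.5 - 63.1 = -8.6.

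Verdicts differ in 6.5%, 9.4%, 10.1% and 12.4% of trials respectively. The sign again depends on the assumed distribution.

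**The case for a change.** The strongest case is that a confirmatory gate deserves the precision the SAP shows elsewhere. Just after the log sentence, 8.1.1 lists four fallback covariance structures in order, and 8.2.6 gives a 3-SD rule for outliers. Restricting, deleting or defining the option would cost a few sentences, SAP section 1 allows revision before lock, and the protocol's permissive wording would not be breached. A second simulation (gamma-Poisson, 40% reduction) also favoured no log: 74-98% power untransformed against 60-94% for ln(score + 1).

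Part of this stands. The text does leave out the logged variable, the criterion and the handling of zeros. The reach of the 8.2.3 note cannot be read off, and a logged [s]iVaw analysis would need matching wording in Table 2-2, section 8 and 8.1.5.

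The comparison with the other rules is weaker. Non-convergence appears when the model with treatment is fitted, and the 3-SD rule is computed within treatment group, so both act where results could steer the choice. The log decision is taken blinded.

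The case for barring the log is also mixed. On the same assumed models it gives up about 20-24 points if dupilumab empties all plugs in a subset, while in the other patterns it avoids losses of up to 29-35 points and gives up at most 2. Which pattern applies is unknown.

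**Conclusion.** No change is called for. This is missing detail in an option that need not be used, and analysts can fill it sensibly. If a mucus score of 0 makes the log impossible, the untransformed change model already written remains the analysis. If [s]iVaw or [s]iRaw proves extremely skewed, the log of the measured value is the natural choice. The SAP's note that the baseline term belongs to the variable analysed then reasonably carries the covariate to the same scale.

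Blinding keeps the choice from following the result, and simulated type I error for the mucus score is about 5% for each fixed form. The possible effect on power is not small, but its direction is not established: -35 to +24 points for the mucus score and about -9 to +5 in the [s]iVaw examples above. All these figures rest on assumed distributions, zero shares, clearing patterns and a borrowed 64% calibration. Restricting or deleting the option is therefore a trade-off with no demonstrated gain, and defining it would only write down what a competent analyst would do. Confirming which endpoints carry the asterisk and naming the logged variable would be good housekeeping before lock.
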